Data Management. Baseline, 5-week, and 6-month survey data will be exported from REDCap as .CSV files, which will be read into SAS version 9.4 (SAS Institute, Cary, NC) on a weekly basis during data collection. Data review and primary data analyses will be performed using SAS version 9.4. [name] will oversee the data management, provide the PIs with reports and summaries on a regular basis, and perform the final analyses.

Sample Size and Study Power Analysis. The primary statistical analysis for Aim 2 will use logistic regression to compare abstinence rates at the 6-month assessment between QL+AR and QLO conditions. Preliminary analyses will be used to identify demographics and tobacco history variables that predict either missing surveys or abstinence around 5 weeks and 6 months. These variables will be used in a multiple imputation model to manage missing data. Based on abstinence rates from quitline/telephone counseling (Fiore et al., 2008; Matkin et al., 2019; Pinero et al., 2020), the estimated 7-day point prevalence abstinence rate around 6 months for the QLO condition is 10%. With 1036 randomized to each condition, power was calculated for the 725 participants expected to achieve 48-hours of abstinence in each condition (to activate the AR app). Power $\geq .80$ to detect an abstinence rate of at least 15% (OR = 1.59) in the QL+AR condition using alpha = .05, a 2-sided test, and allowing 5% of variance in abstinence rates to be accounted for by other variables. A comparable analysis using all 2072 randomized participants (the 1450 who do achieve 48-hours of abstinence plus the 622 who do not) will have lower expected abstinence rates. Estimating that 7% of all QLO participants will be abstinent, power $> .80$ to detect an abstinence rate of at least 10.6% for QL+AR (OR = 1.57) using alpha = .05, a 2-sided test, and allowing 5% of variance in abstinence rates to be accounted for by other variables.

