Data Analysis Overview. Descriptive statistics will be used to review all variables in the study prior to hypothesis testing. Data transformations will be made as needed. Treatment group differences in baseline measures will be assessed and any variable with a group difference of $p < .10$ will be incorporated into analyses focusing on intervention effects. All analyses described below will be performed for those who achieved 48 hours of self-reported abstinence (n=1450) as well as the full sample of those enrolled (N=3590). The former is relevant to assessing the efficacy of the app specifically, whereas the latter will reflect the overall incremental effectiveness of the app from the perspective of the quitline. Full-sample versus AR-sample differences in baseline measures will be evaluated.

To manage missing data, multiple imputation under the Missing at Random assumption will be applied using a Markov Chain Monte Carlo method (Schafer, 1997) via PROC MI in SAS, given the expected nonmonotonic missing data patterns and the expected large number of auxiliary variables (e.g., baseline measures that predict smoking status at follow-up) to be determined by preliminary analyses. The imputation model will

include smoking status around 5 weeks, which is expected to be a primary predictor of smoking status around 6 months.

In addition, any other measures acquired around 5 weeks that are unique predictors of missingness or smoking status around 6 months will be included in the imputation model. Finally, a post hoc approach (Rubin, 1987) will address the possible influence of Missing Not at Random. As done in recent studies (e.g., [name] et al., 2016; Martinez et al., in press), the post hoc adjustment will be small-to-medium in size (akin to Cohen's $d=0.35$) in accordance with missing implies smoking. Twenty data sets will be generated. Therefore, all analyses of the primary outcome will be performed on complete data sets (i.e., intent-to-treat) following multiple imputation.

Analytic Plan for Addressing Specific Aims.

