Aim 2a. The primary test of the efficacy of QL+AR over QLO will use logistic regression on biochemically-confirmed abstinence around 6 months after baseline survey completion. This will be performed on the 20 imputed data sets using those participants who exhibited 48 hours of abstinence (n=1450). The model will include demographics and smoking-related variables that were found to uniquely predict self-reported abstinence at 6 months based on preliminary analyses. A parallel analysis will be performed to evaluate efficacy for all enrolled (N=2072; i.e., beyond those who exhibit the required 48-hour abstinence to engage the AR intervention). A second test of effectiveness will use generalized estimating equations (GEE) with both the 5-week and 6-month abstinence as the outcomes. This approach permits evaluation of a change in abstinence from around 5 weeks to 6 months and an assessment of the intervention at around 5 weeks in the context of the primary outcome (using a timespecific contrast).

Aim 2b. Prospective moderators of the QL+AR intervention will be explored, separately, by extending the analyses described above through the inclusion of the moderator and the moderator x intervention as predictors of the dependent measure. A significant interaction term supports the variable as a moderator, which will be explored by assessing condition differences for each level of categorical moderators and for levels of continuous moderators created via median splits, tertiles, or quartiles. The following baseline measures will be evaluated: sex, nicotine dependence, trait cue reactivity, smoking status during treatment, quitline use, and NRT use.

Prospective predictors of the AR intervention will be evaluated using only participants from the QL+AR arm. Similar to the analyses described above, AR-related variables will be added to a logistic regression model of abstinence at around 6 months that includes demographics and baseline smoking-related variables found to be predictors of abstinence among QL+AR participants. The following variables will be explored: initial cue reactivity, extinction magnitude and latency, indices of treatment engagement, and App coach use.

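### Aim 2b describes continuous moderators through sample-based groups, with the number of cuts left open; estimates at prespecified values from the interaction model already planned would be more precise and would not depend on a later choice

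*Combined protocol and SAP*

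**What the plan says.** The plan for Aim 2b (section 5, Analytic Plan for Addressing Specific Aims) states: "Prospective moderators of the QL+AR intervention will be explored, separately, by extending the analyses described above". Each moderator gets its own model with a main effect and a product with arm. The decision rule is "A significant interaction term supports the variable as a moderator". A moderator that passes is then described by arm differences within each category or, if it is continuous, "for levels of continuous moderators created via median splits, tertiles, or quartiles". Nothing says which of the three splits applies, who chooses it, or whether the choice precedes sight of the results.

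The list is: "The following baseline measures will be evaluated: sex, nicotine dependence, trait cue reactivity, smoking status during treatment, quitline use, and NRT use". Nicotine dependence and trait cue reactivity are the clear continuous baseline measures. The Data Analysis Overview adds: "All analyses described below will be performed for those who achieved 48 hours of self-reported abstinence (n=1450) as well as the full sample". Neither place states a significance level for the interaction tests or a rule for multiple tests, or says which sample leads for Aim 2b.

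**The concern.** Aim 2b is meant to say for whom the app works. Readers will take that answer from the table of arm differences by level, not from the interaction coefficient. Cutting at sample quantiles has two costs.

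- **Precision.** Each level uses a half, a third or a quarter of the participants, and the cut ignores how the moderator varies within a level. The interaction model has already been fitted to everyone and gives the arm effect at any moderator value.
- **Dependence on the cut.** The boundaries depend on the sample, and the number of groups is open. The same significant interaction can be shown as two, three or four levels, and the apparent responders can differ between displays.

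At stake is how a moderator finding is described. The primary comparison is not touched.

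**Working it through.** **Inputs from the plan.** 725 per arm in the 48-hour group; 10% (QLO) v 15% (QL+AR); two-sided .05; 5% of variance taken by covariates. These come from the Sample Size and Study Power Analysis paragraph ("power was calculated for the 725 participants expected to achieve 48-hours of abstinence in each condition"; "using alpha = .05, a 2-sided test, and allowing 5% of variance in abstinence rates to be accounted for by other variables"). For all randomized participants: 1036 per arm, 7% v 10.6%.

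**Assumptions not in the plan.** The moderator is normal and standardized, its interaction is linear on the log-odds scale, it enters the test uncut, and .05 also applies to the interaction tests.

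**1. The plan's own power.** The effective n is 725 × 0.95 = 688.75. The mean proportion is .125, so √(2 × .125 × .875) = .4677 and √(.10 × .90 + .15 × .85) = .4664.

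z = (.05 × √688.75 − 1.96 × .4677) / .4664 = 0.848, which gives power .80. This matches the stated figure.

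**2. Precision within a level.** SE(log OR) = √[1/(n × .10 × .90) + 1/(n × .15 × .85)], and the CI is 1.588 × exp(±1.96 × SE).

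| Level | n per arm | SE | 95% CI around OR 1.59 |
|---|---|---|---|
| All | 725 | 0.162 | 1.16–2.18 |
| Half | 362.5 | 0.229 | 1.01–2.49 |
| Third | 241.7 | 0.280 | 0.92–2.75 |
| Quarter | 181.25 | 0.323 | 0.84–2.99 |

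**3. Group estimate against model-based estimate.** Let V be the variance of the overall log OR. To a first approximation, a group estimate from 1/k of the sample has variance kV, and the model-based estimate at standardized value x has variance V(1 + x²). Take x as the mean of the top group of a standard normal.

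- Top half: x = 0.798, x² = 0.637, ratio = 2/1.637 = 1.22.
- Top third: x = 1.091, x² = 1.190, ratio = 3/2.190 = 1.37.
- Top quarter: x = 1.271, x² = 1.616, ratio = 4/2.616 = 1.53.

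Simulated trials of 1450 participants agree. The SEs were 0.234 (half) v 0.214 (model), a variance ratio of (0.234/0.214)² = 1.20. For the top quartile they were 0.34 v 0.27, a ratio of (0.34/0.27)² = 1.59. Across simulations the range was about 1.2–1.3 for halves and 1.4–1.6 for the top quartile.

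**4. Do the cuts inflate false positives?** In 3000 null trials the uncut interaction test rejected in 5.3%. The cut comes afterwards, so the rate per moderator stays near .05 whichever split follows. It would reach 10.7% only if the interaction itself were tested on the best of the three splits.

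**5. Does the description change with the cut?** Among simulated trials that passed the interaction test by chance, statistical significance in the apparently most responsive group changed with the number of cuts in about 17%. With a true interaction of 0.30 or 0.45 log-odds per SD (assumed), the figure was about 7% and 3%.

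**6. Number of tests.** For six independent tests at .05 under the global null, 1 − 0.95⁶ = .265, with 6 × .05 = 0.30 false findings expected. The two samples are nested and share nearly all expected quitters: in QLO, 10% of 725 = 72.5 and 7% of 1036 = 72.5. Simulated over both samples, the chance is about 31%; twelve independent tests would give 1 − 0.95¹² = 46%.

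**The case against.** The strongest reply is that the interaction test acts as a gate: "A significant interaction term supports the variable as a moderator, which will be explored by assessing condition differences". The split only describes an interaction already found. This stands, and it rules out several stronger readings that a reader might infer.

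- **That the cuts manufacture moderators.** They do not, provided the moderator enters the test uncut. The plan implies this but does not say so. The loss of power from testing the interaction on groups likewise concerns a procedure the plan does not state.
- **That a uniform effect will usually look mixed across levels.** Power for 10% v 15% within a half, third or quarter is only .51, .37 and .29 (with the 5% variance allowance). With a uniform effect, however, the levels are examined only about 5% of the time per moderator.
- **That two samples mean twelve independent tests.** Nesting adds only about 5 percentage points.
- **That a multiplicity correction is required.** The Specific Aims and Aim 2b both call this work exploratory, and the six variables are named in advance. For a 50/50 moderator the ratio of odds ratios detectable with 80% power is already exp(2.80 × 0.323) ≈ 2.5, and a stricter threshold would raise it. Statisticians differ on this trade-off.

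It is also fair to say that the precision gain depends on the model form, is small for halves, and would be partly spent on a curvature term. The cut issue does not arise for sex. None of this justifies leaving the number of cuts open or preferring the less precise display.

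**Conclusion.** The point holds as a fault in how a found moderator is described. The plan fits a model that gives arm effects at any moderator value, then sets it aside for group comparisons whose number is not fixed. Under a normal moderator and linear interaction with 725 per arm, this costs about 20–30% more variance for halves and 40–60% more for the top quartile. A skewed moderator, or a score with few distinct values, would change these figures. The open choice of split adds a dependence on the analyst that is largest when the interaction is a chance finding.

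The roughly 26% chance of at least one false moderator (about 31% over both samples) is a separate caveat. It comes from six unadjusted tests, not from the cuts. It rests on independence, the global null and an inferred .05, since the plan states that level only for its power calculation.

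**What to change.** In Aim 2b:

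1. Delete the wording on splits.
2. State that continuous baseline moderators, such as nicotine dependence and trait cue reactivity, enter the interaction test uncut.
3. Report the arm odds ratio and risk difference with 95% CI from that model at prespecified values, such as the 10th, 50th and 90th percentiles of the pooled baseline distribution.
4. Add a curvature check (a quadratic or spline term).
5. State the significance level for the interaction tests, and present all six moderators as exploratory, each with its interaction estimate and CI whether or not it is significant.

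The percentile display suits baseline measures. Smoking status during treatment, quitline use and NRT use appear to be recorded after randomization and would need their own specification. A Holm step across the six tests is optional and not part of this change.

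The cost is a few sentences in the plan and a few lines of SAS code, with no new data. The small downside is reliance on the model form, which item 4 addresses.

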Assess. Each morning, participants will be prompted to complete a daily diary to assess the following from the previous day: number of cigarettes smoked, NRT use, and tobacco craving. Because ongoing smoking during cue-exposure sessions will be counter-productive to extinction of urges, participants will need to self-report 48 hours of abstinence to advance to Setup. Achieving such short-term abstinence with quitline support/NRT should be feasible for at least 70% of participants (Shiffman et al., 1996; Shiffman et al., 2007).

Setup. Once the abstinence requirement is met, participants will personalize the app, learn the purpose of the app, and practice using AR. First, they will watch a video tutorial explaining the use of cue exposure. They will select their most relevant AR cues and situations in which they most commonly smoke and/or experience high cravings (e.g., upon waking, after meals, when stressed, with alcohol, with coffee, celebrating). They will receive a list of “best practices” for completing AR sessions (e.g., no smoking during sessions). Participants will next receive instruction on using the app for cue-exposure sessions, comprising a short video describing how to place the AR objects, followed by an interactive tutorial with real-time practice.

Recommendations for Use. Recommendations for daily use will be proactively provided, but also available for later review on demand. The app will recommend that participants complete 2-5 AR sessions per day. It will emphasize that the more often they use the app when experiencing craving, the more successful they will likely be in maintaining abstinence.

Extras. Participants will be introduced to all other features of the app: setting up reminder notifications, accessing the progress tracker, access to the App coach, and viewing of rewards.

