The Florida Tobacco Quitline is operated by RVO Health, the largest provider of tobacco cessation quitlines in the U.S. RVO Health's Quit For Life® program is an evidence-based tobacco cessation treatment delivered over phone, web, and text, and is grounded in social cognitive theory and the U.S. Public Health Service clinical guidelines (PHS Guideline, 2008). Quitline coaches use cognitive behavioral therapy, reinforcement, and principles of self-efficacy to promote effective behavior change. The quitline approach includes 5 key elements: setting a quit date, coping with triggers, effectively using medications, tobacco proofing, and social support. Phone counseling for cessation has been evaluated in randomized trials and effectiveness studies (Hollis et al., 2007; Orleans et al., 1991; Stead et al., 2013; Zhu et al., 2002). Individuals who enroll in the quitline's multi-call program receive three phone calls. They are mailed two weeks of NRT after the first phone call, to begin using on their quit date (coinciding with the second call). Participants will be provided with information about the study during their first phone call, and study staff will reach out to enroll participants in the study after receiving their contact information from the Quitline.

Study Arms

Quitline Only (QLO). Participants randomized to the QLO condition will receive an app that administers the daily diary questions for 5 weeks and shows their app and abstinence related progress. They will not receive any treatment via the app. Thus, they will receive usual care via the quitline and complete minimal daily assessments.

Quitline plus AR (QL+AR). Participants randomized to QL+AR will receive the AR app described in Aim 1. Initially, the app will only administer the daily diary questions. Once 48 hours of self-reported tobacco abstinence is achieved, the AR elements of the app will become available (see 4.2). Daily diary questions will continue for 5 weeks. AR extinction trials will occur daily until (1) the participant reports 3 consecutive days of smoking, in which case the AR trials will be suspended until another smoke-free 48 hours are reported, or (2) a

total of 5 weeks have elapsed since the start of app use.

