indicator of treatment engagement. Primary treatment engagement variables of interest that are linked to our theoretical model of extinction and that are related to increased abstinence include: greater completion of the AR sessions (e.g., multiple times per day over several days), conducting the AR sessions in several different locations (to increase generalizability of extinction), and less use of avoidance strategies during the AR sessions (e.g., using distraction or other behaviors to avoid experiencing craving). Avoidance strategies will be assessed at the 5 week survey via a checklist of avoidance strategies and the frequency that they occurred during AR sessions. We will also collect self-reported treatment satisfaction using a modified version of the Client Satisfaction Questionnaire (Attkisson & Greenfield, 1994), the SUS (Brooke et al., 1996; Lewis & Sauro, 2009), and unique items to assess features and functions of the app and the AR experience, including the App coach. Extinction magnitude (degree of craving reduction over time) and latency (time to meeting extinction criteria) will also be derived. For participants who never achieved abstinence during the 5 weeks of app use, thus, never completed AR sessions, versions of the follow-up surveys will omit items specifically related to AR use. For participants who achieved abstinence, but did not complete more than 4 AR sessions, there will be questions at the 5-week survey regarding barriers to completing the AR sessions.

Quitline Usage and App Coaching. Basic information on participant interactions will be provided to the study team from the quitline, including call completion dates, quit status (planned and actual quit dates), and NRT that was shipped. For those in QL+AR, we will track calls completed with an App coach.

Tobacco Abstinence. The primary outcome measure will be 7-day point prevalence abstinence (defined as self-report of no combustible tobacco use in the past 7 days; Piper et al., 2020) around 6 months post-baseline. Reported abstinence will be confirmed in approximately 40% of self-reported abstinent participants using a saliva cotinine level cut-off of <10 ng/ml (Benowitz et al., 2020). Cotinine analysis using ELISA assay will be conducted by Salimetrics (Carlsbad, CA).

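### Aim 2b lists smoking status during treatment as a baseline moderator, but it is recorded after app use starts, later status can respond to the app, and it controls AR access in QL+AR only

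*Combined protocol and SAP*

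**What the plan says.** Section 5, Aim 2b, introduces its list of moderators with the sentence "The following baseline measures will be evaluated: sex, nicotine dependence, trait cue reactivity, smoking status during treatment, quitline use, and NRT use". Each is tested separately by adding the variable and its product with arm to the Aim 2a models. The reading rule is: "A significant interaction term supports the variable as a moderator, which will be explored by assessing condition differences for each level of categorical moderators". Section 1, Aim 2b, names the same six variables without calling them baseline.

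Other parts of the protocol fix when smoking status is observed and what it does:

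- Section 3.2: randomisation comes first, then the baseline survey, then app download.
- Section 4.2, Assess: users each morning "complete a daily diary to assess the following from the previous day: number of cigarettes smoked, NRT use, and tobacco craving". Section 4.3 runs the diary for 5 weeks.
- Section 4.2, Recommendations for Use: users are told that "the more often they use the app when experiencing craving, the more successful they will likely be in maintaining abstinence".
- Section 4.3, Study Arms, QL+AR: "Once 48 hours of self-reported tobacco abstinence is achieved, the AR elements of the app will become available". After three smoking days in a row the rule reads "in which case the AR trials will be suspended until another smoke-free 48 hours are reported". QLO has no such rule, because its app delivers no treatment.
- Section 4.4 describes a group in these terms: "For participants who never achieved abstinence during the 5 weeks of app use, thus, never completed AR sessions".
- Section 5, Aim 2a: "A second test of effectiveness will use generalized estimating equations (GEE) with both the 5-week and 6-month abstinence as the outcomes".

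None of the text available gives smoking status during treatment a definition, a data source or a time window.

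**The concern.** A moderator analysis asks for whom the treatment works. It can answer that when the moderator is fixed before treatment can act on it, because randomisation then keeps the arms comparable within each level. Smoking status during treatment fails this condition in two separate ways.

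First, later status may be a result of the app. If AR keeps more people abstinent, the QL+AR abstainers include people with a poorer prognosis who would otherwise have lapsed, and the people still smoking in QL+AR are a harder-to-treat remainder. Each level then compares unlike groups.

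Second, in QL+AR the status decides whether AR is delivered at all. A smaller effect among those who smoke during treatment could be a real interaction, yet mean only that AR was locked or suspended for them.

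Either result could be reported as showing who benefits, in a trial whose Aim 3 is meant to guide quitline adoption.

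**Working it through.** **1. Timing.** The baseline survey also follows randomisation, so that order alone does not settle the matter. What does is that diary status is recorded after the app is in use. Two codings must be kept apart.

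- *First attainment of 48 hours abstinent.* Before unlock, the QL+AR app only runs the diary. AR sessions therefore cannot affect this event.
- *Later status.* Lapse, suspension and 5-week smoking come after AR can open, and AR is meant to reduce them. The 5-week version overlaps an outcome of the Aim 2a GEE analysis.

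**2. Ever/never coding, full sample.** Inputs are from section 5, Sample Size and Study Power Analysis, with the full sample taken as 2072 (the Data Analysis Overview prints 3590 in one place).

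- The plan's own split reproduces: 0.70 × 1036 = 725.2, and 2072 − 1450 = 622, so 622 / 2 = 311 per arm never reach 48 hours.
- The plan's 7% for all QLO equals 0.70 × 10%, which leaves essentially no six-month abstainers in the never group: 0.07 × 1036 − 0.10 × 725 = 72.52 − 72.50 = 0.02.
- For QL+AR: 0.106 × 1036 − 0.15 × 725 = 109.82 − 108.75 = 1.07.

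These are differences of rounded figures. Reading 10.6% as 10.55% to 10.65% moves 1.07 between 0.55 and 1.58. Reading 7% as 6.5% to 7.5% moves 0.02 between −5.2 and 5.2. The safe inference is that events in this level will be very few and its odds ratio hardly estimable.

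**3. Later status: size of the selection effect.** The documents give no figures for this, so the following is an illustration on assumptions.

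- U is a standard normal prognostic factor.
- On-treatment abstinence: logit P(M=1) = a_T + uU, with a_T set by arm.
- Six-month abstinence: logit P(Y=1) = c + bM + uU + dT, with the same d in both levels.
- Assumed: u = 1, b = 1.8, QLO on-treatment abstinence 30%.
- From the plan: c gives 7% in QLO, and d is re-solved each time to give 10.6% in QL+AR.

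The no-selection odds ratio standardises QL+AR to the QLO distribution of U within the same level. The selection factor is the as-planned odds ratio divided by the no-selection one. Pairs are smokers / abstainers.

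| QL+AR on-treatment abstinence | exp(d) | No-selection OR | OR as planned | Selection factor |
|---|---|---|---|---|
| 30% (no shift) | 1.76 | 1.74 / 1.65 | 1.74 / 1.65 | 1.00 / 1.00 |
| 33% | 1.65 | 1.63 / 1.55 | 1.59 / 1.51 | 0.975 / 0.975 |
| 36% | 1.55 | 1.53 / 1.47 | 1.46 / 1.40 | 0.951 / 0.951 |
| 42% | 1.39 | 1.38 / 1.33 | 1.24 / 1.21 | 0.904 / 0.908 |
| 50% | 1.23 | 1.22 / 1.20 | 1.03 / 1.02 | 0.846 / 0.855 |

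The fall in exp(d) down the table is mediation, not bias. The gap between exp(d) and the no-selection value is non-collapsibility.

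Sensitivity to u: with u = 0 there is no selection effect; u = 0.5 gives 0.99 at 36% and 0.95 at 50%; u = 2 gives 0.855 / 0.882 at 36% and 0.60 / 0.69 at 50%. Changing b to 1.0 or 2.5 leaves the 42% factors at 0.90 to 0.91.

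**4. Effect on the interaction.** The ratio of the two factors is 0.951/0.951 = 1.00, 0.908/0.904 = 1.00 and 0.855/0.846 = 1.01. Only the extreme case (u = 2, 30% to 50%) reaches 0.69/0.60 = 1.15. For b = 1.8 the planned interaction test is significant in 5% to 6% of trials, about the nominal rate.

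**5. The 48-hour-abstainer set** (10% v 15%; assumed QLO on-treatment abstinence 30%/70% = 43%). Factors are 0.968 / 0.971 at 47%, 0.937 / 0.944 at 51% and 0.870 / 0.887 at 60%. Everyone in QL+AR has unlocked AR here, so of the delivery rule only suspension remains.

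**The case against.** The strongest reply is that little of consequence follows. Aim 2b is exploratory. Only a significant interaction triggers the within-level step, and the selection mechanism almost never produces one. Its size rests wholly on assumptions. Even with a shift from 30% to 50%, the 95% intervals for the as-planned odds ratios are 0.46 to 2.33 (smokers) and 0.72 to 1.47 (abstainers), so sampling error swamps the bias. The plan also repeats every analysis among 48-hour abstainers, which removes the never-unlocked group. All of this stands, and it limits the point. It does not make the baseline label correct, and it does not answer the delivery-rule problem, which can yield a true interaction that is then misread.

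Three stronger readings are tempting and not supported:

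- *AR alters every form of on-treatment smoking.* It cannot alter first attainment of 48 hours, which precedes unlock.
- *The 0.02 and 1.07 events forecast a contrast between arms.* They come from separately stated, rounded rates; 15% and 10.6% are detectable rates, not a joint prediction.
- *Quitline use and NRT use are equally compromised.* No app effect on quitline use is described. One on NRT use is plausible, because Table 1 restricts nicotine products other than the patch before sessions and App coaching covers NRT, but little coach use is expected. Some use of both can precede randomisation.

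Section 5 also mentions a Statistical Design and Power attachment. If it is a separate document, it might define the variable.

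**Conclusion.** The point holds for smoking status during treatment. The plan calls it baseline and would read its interaction with arm as moderation, although it is observed during app use, later status is an intended target of the app, and it governs AR access in one arm only.

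The two mechanisms differ in weight. Selection within levels needs both a shift in later status and a shared prognostic factor. With a factor log odds ratio of 1 and on-treatment abstinence rising from 30% to between 33% and 50%, it multiplies the within-level odds ratios by about 0.98 down to 0.85. Because it acts nearly equally in both levels, a reader should not infer that selection would create a false moderator. The delivery rule needs no such assumption. With ever/never coding, about 311 people per arm fall in a level where QL+AR participants never receive AR; with later status, suspension plays a similar part.

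This should be corrected before analysis. A reader might infer that the main result is at risk. It is not, because the primary test does not use this variable as a moderator.

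**What to change.** In section 1 (Aim 2b) and section 5 (Aim 2b):

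- Remove smoking status during treatment from the moderator list. Define it, with its source (diary or 5-week survey) and time window.
- Report it by arm as a post-randomisation variable, either descriptively or as a mediator in the mediating-variables paper already listed in the section 6 timeline. Drop the within-level arm comparisons for it.
- State that the baseline values of the HSI and the WISDM cue-exposure subscale are the ones used, because section 4.4 repeats these measures at each assessment.
- For quitline use and NRT use, remove the baseline label from any part that follows randomisation, and say that arm-by-variable results for that part are descriptive and do not show who benefits.

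A pre-randomisation version of the last two is optional and may be uninformative. Everyone hears of the study in the first quitline call, and NRT is mailed after that call, so shipment before randomisation may mainly reflect how quickly staff call back.

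The cost is wording in two sections and no new data. The optional version would need the randomisation date matched to quitline records, and a mediation analysis would be extra work. One exploratory moderator analysis is lost and two are relabelled.
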